9.3.1 DISEASE PROGRESSION

Discontinuation of treatment due to either progression or deterioration due to the primary malignancy should be recorded on the Treatment Discontinuation CRF as "Disease Progression" and not as an AE or an SAE, unless the event meets the SAE reporting criteria described in [Section 9.4](#).

In addition to an increase in M-protein, natural disease progression of multiple myeloma typically displays specific clinical signs and symptoms such as elevated Calcium, Renal insufficiency, Anemia, and Bone disease (known as the “CRAB” features) (Durie 2006). Signs and symptoms clearly associated with progression should not be listed as AEs unless judged by the Investigator to be atypical or accelerated or if the Investigator considers the sign or symptom to be caused by the study drug. If there is any uncertainty regarding causality, the event should be recorded in the CRF as an AE or SAE as appropriate.

All deaths during treatment or within 30 days of the last dose of study drug are to be reported as SAEs (see Section 9.4). The corresponding entry for progression-related deaths on the AE CRF should use the verbatim term “Disease Progression” rather than the specific sign or symptom that may have been the immediate cause of death. Additional details of the event (such as the primary and contributory causes of death) should be reported on the Death CRF.

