STUDY TREATMENT	
Carfilzomib will be administered intravenously (IV), using the same method, dose level and frequency as administered in the last cycle of the subject's previous carfilzomib study; carfilzomib doses will be administered on Days 1, 2, 8, 9, 15, and 16 of a 28-day cycle (or the same dose level and frequency as administered at the last visit of the prior carfilzomib study) until disease progression and discussion with the Onyx Medical Monitor, diagnosis of new malignancy, unacceptable toxicity, Investigator discretion, voluntary withdrawal, or commercial availability of carfilzomib. Each dose will consist of Carfilzomib for Injection administered on a mg/m² basis. Subjects with a body surface area (BSA) > 2.2 m² will receive a dose based upon a 2.2 m² BSA. Dosing will be continued or modified based upon clinical and laboratory findings.
 
Decreased carfilzomib dosing frequency to include dosing on Days 1, 2, 15 and 16 (eg, every other week dosing schedule), will be permitted at the discretion of the Investigator; the Onyx Therapeutics Medical Monitor may be consulted as needed. Carfilzomib dose reductions for toxicity, to a minimum dose of 11 mg/m², will be permitted following discussion with the Medical Monitor, as needed. Missed doses of carfilzomib will not be made up.
 
Dose escalations above the original dose level are permitted.
 
For subjects with evidence of disease progression, the Onyx Medical Monitor must be consulted prior to the dose escalation or termination from study.
 
Acyclovir or valacyclovir should be given to all subjects with a history of herpes simplex or zoster, per institutional prophylaxis guidelines, unless contraindicated.

PRIMARY ENDPOINT	
• Safety
SECONDARY ENDPOINTS	
• Overall Survival (OS)• Progression Free Survival (PFS)• Time to Progression (TTP)

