9.4 SERIOUS ADVERSE EVENTS DEFINITIONS

An SAE is one that meets one or more of the following criteria:

- Death
- Life threatening experience defined as any adverse experience that places the subject, in the view of the Investigator, at immediate risk of death at the time of occurrence; ie, it does not include a reaction that, had it occurred in a more severe form, might have caused death.
- Requires inpatient hospitalization or prolongation of an existing hospitalization (except scheduled hospitalizations for non-acute, unrelated cause such as an elective surgery)
- Results in persistent or significant disability/incapacity
- Is a congenital anomaly/birth defect in the offspring of an exposed subject
- Important medical events that may not result in death, be life threatening, or require hospitalization, may be considered an SAE when, based upon appropriate medical judgment, it jeopardizes the subject and may require medical or surgical intervention to prevent one of the outcomes listed in this definition.

Any death occurring within 30 days of the subject receiving study drug, regardless of the subject having discontinued from the study must be reported to the sponsor as an SAE.

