9.5 SERIOUS ADVERSE EVENT REPORTING AND DOCUMENTATION REQUIREMENTS

Onyx Therapeutics, Inc. must be notified by telephone or fax of the occurrence of any SAE within 24 hours of the Investigator, designee, or site personnel knowledge of the event.

To report an SAE, call or fax an SAE form to:

Attn: i3 Research
[contact]
SAE [contact]
E-mail: [contact]

Telephone reports must be followed by a written report within 24 hours. Follow-up reports must be submitted in a timely fashion as additional information becomes available.

The Investigator is responsible for notifying the Institutional Review Board (IRB) or Independent Ethics Committee (IEC) in accordance with local regulations, of all SAEs. The sponsor may request additional source documentation pertaining to the SAE sent to Onyx. If a subject is permanently withdrawn from the study because of a SAE, this information must be included in the initial or follow-up SAE report form as well as the Study Discontinuation CRF.

All SAEs occurring from the time that the subject signs consent for study participation or up to 30 days after the last administered dose of study drug will be reported. All SAEs regardless of relationship to study drug must be followed to resolution or to stabilization if improvement or resolution is not expected.

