10.2.1 PRIMARY ENDPOINTS (SAFETY)

- Reported peripheral neuropathy AEs (all Grades)
- Reported Grades 3 and 4 AEs
- SAEs
- Grades 1 through 4 AEs leading to a missed carfilzomib dose or a carfilzomib dose reduction or discontinuation

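### Section 9.3.1 keeps non-fatal serious signs of progression off the AE record while Sections 9.3 to 9.5 require them, so the primary SAE count can be understated or differ by site

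*Protocol*

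**What the plan says.** Protocol Section 9.3.1 has three paragraphs, and each deals with a different thing.

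- **Paragraph 1** is about stopping treatment: "Discontinuation of treatment due to either progression or deterioration due to the primary malignancy should be recorded on the Treatment Discontinuation CRF". Such a discontinuation is not entered as an AE or SAE unless the event meets Section 9.4.
- **Paragraph 2** is about signs and symptoms. It names hypercalcaemia, renal insufficiency, anaemia and bone disease as typical of myeloma progression, then says: "Signs and symptoms clearly associated with progression should not be listed as AEs unless judged by the Investigator to be atypical or accelerated". A second exception follows in the same sentence: "if the Investigator considers the sign or symptom to be caused by the study drug". The next sentence adds a third: "If there is any uncertainty regarding causality, the event should be recorded in the CRF as an AE or SAE as appropriate".
- **Paragraph 3** makes every death on treatment or within 30 days of the last dose an SAE. It gives the verbatim term for progression-related deaths.

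The general rules are these. Section 9.3 lists all SAEs among the events to report and puts them on both the AE CRF and the SAE form. It also treats any laboratory finding that needs therapeutic intervention as an AE. Section 9.4 counts as serious an event that "Requires inpatient hospitalization or prolongation of an existing hospitalization", excepting only scheduled admissions for a non-acute, unrelated cause. Section 9.5 requires reporting of SAEs from consent to 30 days after the last dose, and adds: "All SAEs regardless of relationship to study drug must be followed to resolution".

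SAEs are one of the four primary safety endpoints (Protocol 10.2.1, SAP 3.1), next to "Reported Grades 3 and 4 AEs". SAP 7.6.1 plans a table of serious treatment-emergent events and has no rule for events due to progression.

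**The concern.** Paragraphs 1 and 3 of Section 9.3.1 each deal with seriousness. Paragraph 2 does not, so a site can reasonably take the omission as intended. A site that applies paragraph 2 would leave out a hospitalisation clearly due to progression. A site that applies Sections 9.4 and 9.5 would report it.

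The gap matters here because progression need not end treatment. The synopsis says: "For subjects with evidence of disease progression, the Onyx Medical Monitor must be consulted prior to the dose escalation or termination from study". Section 1.5 foresees dose escalation for subjects who progress, and Section 6.4.2 allows further antitumour agents when progression is a concern. SAP 5.5 and 7.7.2 reset the baseline and recalculate PFS after such changes. A progressing subject who stays on carfilzomib falls outside paragraph 1 and its SAE exception.

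At stake is a primary endpoint in a single-arm study with about 50 sites. No control arm shares the same recording habits, and an event that was never entered cannot be restored at analysis.

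**Working it through.** The plan gives no figure to reproduce, so the check sets the rules side by side. All cases below start within the reporting window.

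| Case | 9.3.1 para 1 | 9.3.1 para 2 | 9.3.1 para 3 | 9.3 to 9.5 | Result |
|---|---|---|---|---|---|
| A. Non-fatal, serious, clearly progression, ends treatment | SAE exception applies | Not listed | Silent | Report | Paragraph 1 gives an answer; paragraph 2 still contradicts it |
| B. As A, but treatment continues | Silent | Not listed | Silent | Report | Unresolved conflict |
| C. Death on treatment or within 30 days | Exception if it ends treatment | Signs not listed | SAE, term given | Report | Resolved |
| D. Cause uncertain, or drug suspected | Not decisive | Record | Silent | Report if in a listed class | No conflict |
| E. Clinical sign, Grade 3-4, not serious, clearly progression | No grade exception | Not listed | Silent | General rule: all Grade 3-4 AEs | Readable as a specific carve-out |
| F. Laboratory finding needing treatment, clearly progression | Not decisive | Not listed | Silent | 9.3: an AE | Conflict |

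Case B is the main point. Hospitalisation for hypercalcaemia at progression, with carfilzomib continued, meets Section 9.4. Sections 9.3 and 9.5 then require it to be reported and entered on the AE CRF, while paragraph 2 says not to list it as an AE.

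Case F is the secondary point. Anaemia that is transfused or calcium that is treated is an AE by the Section 9.3 sentence and not an AE by paragraph 2. It bears on a primary endpoint when it is Grade 3-4, serious, or leads to a missed dose, dose reduction or discontinuation, because Section 9.3 collects only those classes besides neuropathy.

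**Scale.** Let n be the number of subjects in the denominator and k the number whose only SAE is a case-B event left unrecorded. The SAE incidence is then too low by 100 × k / n percentage points.

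- Overall, n is about 100 (Protocol 10.5, SAP 2.3). For k = 1 the shift is 100 × 1 / 100 = 1 point.
- The documents do not give k. Assuming 1 to 10, the shift is 1 to 10 points.
- By disease cohort (SAP 7.6), n is smaller and is not given. Assuming cohorts of 50 or 25, each such subject moves the figure by 100 / 50 = 2 or 100 / 25 = 4 points.

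A subject who has another recorded SAE does not change the subject-level incidence, but the event is still missing under its own preferred term.

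**The case against.** The best defence is that paragraph 2 speaks only of AEs, whereas paragraph 1 names both AEs and SAEs. Read with Section 9.5, paragraph 2 might leave the SAE route open, or mean that the serious event is entered as disease progression instead of the individual sign. That reading is sensible, but the protocol gives that term only for deaths, and Section 9.3 puts SAEs on the same AE CRF from which paragraph 2 keeps the sign.

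Four further limits on the point stand.

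- **Section 9.3.1 does not ignore seriousness.** A reader might infer that the whole section bars serious events. It does not: paragraphs 1 and 3 provide for them, and doubtful cases are recorded. The gap is confined to non-fatal events clearly due to progression.
- **Overlap with drug toxicity is largely covered.** Section 1.2 reports anaemia and raised creatinine with carfilzomib, and both resemble named progression features. A reader might infer that drug toxicity is being hidden. The drug-causation and uncertainty clauses send such events to the record.
- **The Grade 3-4 endpoint is not generally contradicted.** Section 9.3.1 sits under 9.3, and a specific carve-out for non-serious signs is a permissible choice. Only events that are also serious and treated laboratory findings collide.
- **The frequency is unknown.** Confirmed progression is a listed reason to stop (Section 3.4), AE collection ends when a new anti-cancer therapy starts (Section 9.3), and the named features are those of myeloma only. Nothing says how often subjects continue after progression.

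The study tests no hypothesis (Section 10.1) and plans no comparison between sites, so no decision threshold is at risk.

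**Conclusion.** The concern holds for non-fatal events that meet Section 9.4 and are clearly due to progression, above all in subjects who stay on carfilzomib. One rule excludes them and the others require them. The primary SAE count can therefore be understated or vary with site practice. A similar contradiction exists for laboratory findings that need treatment.

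The size is about 1 percentage point of overall SAE incidence per affected subject at about 100 subjects, and more within a disease cohort. This assumes that the event is the subject's only SAE and that the site follows paragraph 2. A reader might build a larger total from assumed progression and hospitalisation rates. The documents supply no such rates, and a total of that kind would also need every site to follow paragraph 2. The direction of the error is clear, but its total is not.

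**What to change.** **Protocol 9.3.1, paragraph 2.** Add a sentence on these lines: *This exemption does not apply to an event that meets Section 9.4; record it as an SAE and flag it as attributed to disease progression.* State the verbatim term for such non-fatal events. Either the specific sign or a progression term would serve, provided that one is prescribed.

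**Protocol 9.3 and 9.3.1.** Reconcile paragraph 2 with the sentence on laboratory findings that need intervention, saying which prevails when the finding is clearly due to progression. The carve-out for non-serious clinical signs can stay, whatever their grade.

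**SAP 7.6.1.** Present the serious treatment-emergent event table with and without flagged events, by disease cohort and overall.

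The cost is a short amendment, some additional SAE entries, one CRF flag and an extra table column. The headline SAE figure may rise, but the figure without flagged events stands next to it. The change concerns recording only and does not affect treatment. It works forward: serious events already left out could be recovered only by querying the sites.

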9.4 SERIOUS ADVERSE EVENTS DEFINITIONS

An SAE is one that meets one or more of the following criteria:

- Death
- Life threatening experience defined as any adverse experience that places the subject, in the view of the Investigator, at immediate risk of death at the time of occurrence; ie, it does not include a reaction that, had it occurred in a more severe form, might have caused death.
- Requires inpatient hospitalization or prolongation of an existing hospitalization (except scheduled hospitalizations for non-acute, unrelated cause such as an elective surgery)
- Results in persistent or significant disability/incapacity
- Is a congenital anomaly/birth defect in the offspring of an exposed subject
- Important medical events that may not result in death, be life threatening, or require hospitalization, may be considered an SAE when, based upon appropriate medical judgment, it jeopardizes the subject and may require medical or surgical intervention to prevent one of the outcomes listed in this definition.

Any death occurring within 30 days of the subject receiving study drug, regardless of the subject having discontinued from the study must be reported to the sponsor as an SAE.

9.5 SERIOUS ADVERSE EVENT REPORTING AND DOCUMENTATION REQUIREMENTS

Onyx Therapeutics, Inc. must be notified by telephone or fax of the occurrence of any SAE within 24 hours of the Investigator, designee, or site personnel knowledge of the event.

To report an SAE, call or fax an SAE form to:

Attn: i3 Research
[contact]
SAE [contact]
E-mail: [contact]

Telephone reports must be followed by a written report within 24 hours. Follow-up reports must be submitted in a timely fashion as additional information becomes available.

The Investigator is responsible for notifying the Institutional Review Board (IRB) or Independent Ethics Committee (IEC) in accordance with local regulations, of all SAEs. The sponsor may request additional source documentation pertaining to the SAE sent to Onyx. If a subject is permanently withdrawn from the study because of a SAE, this information must be included in the initial or follow-up SAE report form as well as the Study Discontinuation CRF.

All SAEs occurring from the time that the subject signs consent for study participation or up to 30 days after the last administered dose of study drug will be reported. All SAEs regardless of relationship to study drug must be followed to resolution or to stabilization if improvement or resolution is not expected.

9.6 PREGNANCY

The subject must immediately inform her doctor:

- If she becomes pregnant while taking the drug
- If she misses her menstrual period, or experiences unusual menstrual bleeding
- If she stops using birth control
- If she thinks, FOR ANY REASON, that she may be pregnant
- The subject understands that if her doctor is not available, she can call [name] for information on emergency contraception

If a subject or spouse or partner of a subject becomes pregnant while enrolled in this clinical trial or up to 3 months following administration of carfilzomib, Onyx must be notified within 24 hours of the Investigator, designee, or site personnel learning of the pregnancy. If the subject is pregnant, carfilzomib and all other study drug(s) must be withheld until the Medical Monitor is notified, and the case is discussed. Subjects, spouses, or partners will be followed through the outcome of the pregnancy. The Investigator will be required to complete a Pregnancy Information Form and fax the information to:

Attn: i3 Research
[contact]
SAE [contact]
E-mail: [contact]

10 STATISTICAL CONSIDERATIONS

This section outlines the statistical analysis strategy and procedures for the study. Specific details of the primary and key secondary analyses will be provided in the Statistical Analysis Plan (SAP). If, after the study has begun but prior to the final analysis, changes are made to the protocol that affect principal features of the primary or key secondary analyses, then the protocol and/or SAP will be amended, as required. Any other changes made to the planned analyses after the protocol and SAP have been made final, along with an explanation as to when and why they occurred, will be listed in the Clinical Study Report (CSR) of the study. Post hoc exploratory analyses will be clearly identified in the CSR as such.

10.1 OBJECTIVES/HYPOTHESES

The objectives of the study are stated in [Section 2](#). The present protocol will not test any prespecified hypotheses, but will summarize safety and disease response data so that an assessment of each may be made.

10.2 ANALYSIS ENDPOINTS

The safety and disease response endpoints that will be evaluated are listed below, followed by descriptions of the derivations of selected endpoints.

10.2.1 PRIMARY ENDPOINTS (SAFETY)

- Reported peripheral neuropathy AEs (all Grades)
- Reported Grades 3 and 4 AEs
- SAEs
- Grades 1 through 4 AEs leading to a missed carfilzomib dose or a carfilzomib dose reduction or discontinuation

10.2.2 SECONDARY ENDPOINTS (EFFICACY/DISEASE RESPONSE)

- Overall survival (OS)
- Progression-Free Survival (PFS)
- Time to Progression (TTP)

10.3 ANALYSIS POPULATIONS

10.3.1 SAFETY ANALYSIS

The safety population consists of all enrolled subjects who received at least 1 dose of carfilzomib after enrollment in PX-171-010.

10.3.2 DISEASE RESPONSE ANALYSIS

The Full Analysis Set (FAS) population will serve as the primary population for the analysis of the disease response data in this study. The FAS population is a subset of all enrolled subjects, with subjects excluded for the following reasons:

- No post-baseline endpoint data subsequent to at least 1 dose of study treatment on the PX-171-010 protocol (applicable only to PX-171-008 subjects).
- Lack of baseline data for those analyses that require baseline data

10.4 STATISTICAL METHODS

10.4.1 SAFETY ANALYSIS

Safety and tolerability will be assessed by clinical review of all relevant parameters associated with (1) peripheral neuropathy (all Grades) (2) all reported Grade 3 and 4 AEs, (3) Grades 1–4 AEs resulting in a missed carfilzomib dose, dose delay or discontinuation, and (4) reported SAEs.

Treatment-emergent AEs are defined as AEs that start on or after the first day study treatment is administered and within 30 days of the last administration of study treatment.

AEs will be summarized by the number and percentage of subjects who experienced the event, according to system organ class and preferred term. A subject reporting multiple cases of the same AE will be counted once within each system organ class and similarly counted once within each preferred term. Unless otherwise specified, the denominator for these calculations will be based on the number of subjects in each disease cohort (solid tumor or MM) who receive at least 1 administration of carfilzomib on the extended study, irrespective of the total number of doses or treatment cycles administered. These conventions will be appropriately modified to calculate AE incidence rates separately for each cycle that study therapy is administered. AE incidence rates may also be calculated based on other measures of subject exposure (eg, total number of treatment cycles administered). AEs will also be summarized by NCI-CTCAE Version 3.0 severity grade and by relationship to each study drug. For AEs not adequately addressed by the NCI-CTCAE, the severity grading described in [Section 9.1](#) may be used (see [Table 3](#)). Additional summaries may also be provided for SAEs, and events resulting in the permanent discontinuation of therapy. Summaries will be provided by disease cohort. All AEs will be included in individual subject listings.

10.4.2 DISEASE RESPONSE ANALYSIS

The analysis of disease response will be based on the FAS populations defined in [Section 10.3.2](#). The assessment of disease response will be based on duration of OS, PFS, and TTP. For patients previously enrolled in PX-171-008, response may be first noted in PX-171-010. Durations will be calculated from the date of disease response documented in the subjects' prior carfilzomib protocol, or in PX-171-010 for subjects previously enrolled in PX-171-008, to the first documentation of the endpoint's occurrence in the extended trial.

Depending on the completeness of the available follow-up data, analysis of each endpoint will be performed based on the Kaplan-Meier method. The date of progression will be determined using the progression criteria described in [Appendix D–E](#). The date of censoring for subjects who end the study without documented progression will correspond to the date the last disease assessment was performed. Analysis will be performed separately by disease cohort (MM or solid tumor).

